6.4. Data Analysis

6.4.1. Primary Analyses

We will conduct primary analyses to assess the effect of the randomized interventions on drug concentrations at 9-months post-randomization by 1) comparing the first-stage intervention options on TFV-DP levels at the 9-month visit; 2) comparing the second-stage intervention options on TFV-DP levels at the 9-month visit among participants classified as “non-responders” to the initial intervention; and 3) comparing the four adaptive intervention strategies described in Table 1.

For the analyses of first-stage intervention options, logistic regression will be used to assess effect of the each primary randomized intervention on 9-month adherence by comparing TFV-DP levels in Groups 1-3 versus Groups 4-6 shown in Figure 1B on page 10. For the analyses of second-stage intervention options among non-responders, logistic regression will also be used to assess the effect of the intensified adherence intervention (second randomization) within each arm of the first randomization, and in the absence of interaction, pooled across the first randomization (Groups 2 and 5 versus Groups 3 and 6). For analyses comparing the adaptive intervention approaches, each of the 4 overall strategies (2 initial x 2 intensification interventions in non-responders) will be ranked by their overall adherence response (Table 3), with inverse-probability weighting and standard errors taking into account that women who respond to their first-assigned treatment are consistent with *two* of strategies embedded within our SMART design and over-represented in our analysis datasets. Because of the high expected post-randomization drop-out before M1, we will adjust for confounders of PrEP continuation and adherence and M1 drop-out in the analysis.

Table 3. Combination of adherence intervention strategies in SMART design. [Note that under each of the four strategies embedded in our trial design, young women who are adhering (“responding”) will continue to receive their originally-assigned method of support (i.e., WhatsApp groups or weekly two-way SMS).]

Standard of care brief counseling and one-way SMS reminder messages with WhatsApp peer support, followed by quarterly drug level counseling for non-responders
Standard of care brief counseling and one-way SMS reminder messages with WhatsApp peer support, followed by monthly visits with problem-focused counseling for non-responders
Standard of care brief counseling and one-way SMS reminder messages with two-way SMS support, followed by quarterly drug level counseling for non-responders
Standard of care brief counseling and one-way SMS reminder messages with two-way SMS support, followed by monthly visits with problem-focused counseling for non-responders

6.4.2. Secondary Analyses

The primary analyses will be repeated to assess the intervention effects on dried blood spot drug concentrations above 700 fmol/punch at 2 months. Given the long half-life for TFV-DP, gradients of cumulative adherence can also be estimated, such as those described in iPrEX OLE as follows: Below limit of quantitation (BLQ, no doses), BLQ to 349 fmol/punch (fewer than two tablets per week), 350–699 fmol/punch (two or three tablets per week), 700–1249 fmol/punch (four to six tablets per week), and ≥ 1250 fmol/punch (daily dosing). We will also assess the intervention effects on continuously measured TFV-DP concentrations (measured in dried blood spots) Months 2 and 9.

The correlates of response (PrEP adherence based on drug levels) at 2 and 9 months will be assessed using logistic regression modelling, evaluating demographic, behavioral, perceived risk, stigma, self-efficacy, relationship power, transactional sex, IPV, and alcohol use and PrEP adherence by intervention strategy. We will also assess whether level of engagement with the primary intervention (WhatsApp and SMS) is a mediator in the pathway between intervention assignment and PrEP drug levels at Months 2 and 9.

Survival analysis will be used to assess the effect of the adherence strategies as well as individual characteristics (demographics, etc.) on time to PrEP discontinuation for those who choose to stop PrEP before 9 months.

Sensitivity analyses will be performed to assess whether loss-to-follow up is covariate-dependent, and if so, all analyses will be rerun using weighting to account for potentially informative drop-out. Secondary analyses will also explore the possibility of a WhatsApp peer group effect, as young women interacting with one another through the intervention may exhibit correlated outcomes.

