4.2.4.1. Intervention: Monthly counseling visits

Women who are randomized to continue monthly visits will have visits at months 4, 5, 7, and 8 that are focused on counseling. During these visits, women will receive SOC counseling that is tailored to identify problems impacting adherence, generate alternative solutions, make decisions about the alternatives, and collaboratively decide on a plan regarding how to implement the solutions. Additionally, they will have special issue counseling that explores their experiences with intimate partner violence, mental health issues such as depression and anxiety, and drug and alcohol use. Counselors will keep a progress note for each session. Counseling sessions may be audio-recorded to ensure fidelity to counseling messages and these audio-recordings will be reviewed by study team members in the U.S.. Women in this arm will have all procedures listed in 4.2.5 at their 3, 6, and 9month visits.

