4.6. Post-exposure prophylaxis

In the event of sexual assault or possible HIV exposure and if the participant reports inconsistent PrEP use, post-exposure prophylaxis (PEP) will be offered in accordance with local guidelines for one month. PrEP will be discontinued during the one month of PEP, and restarted following repeat HIV testing to exclude possible HIV seroconversion.

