6.0 STATISTICAL CONSIDERATIONS

6.1. Review of Study Design

SMART design to evaluate response to scalable adherence strategies. At enrollment, women will be randomized to either the SOC adherence support plus WhatsApp groups, to provide social support, or SOC adherence support plus weekly two-way SMS messages, to triage and provide additional counseling to manage side effects, adherence issues, or any other concerns. All participants will attend monthly visits for the first 3 months of follow-up and will receive periodic one-way reminder SMS messages about upcoming clinic appointments. In both groups, intracellular tenofovir drug levels based on DBS collected at 2 months will be used as an objective measure of adherence. At the Month 3 visit, women who are classified as "responders" (those with high adherence, based on a TFV-DP threshold of 500 fmol/punch measured at the Month 2 visit) will continue with the SOC counseling and their initial randomization of either two-way SMS or WhatsApp groups but they will be switched to a quarterly visit schedule. Non-responders (those with low adherence based on the Month 2 visit drug levels) will be randomized to more intensive adherence support – monthly visits for SOC adherence and special issue counseling or quarterly visits with drug level feedback at 3 and 6 months in addition to their initial randomization arm intervention (two-way SMS or WhatsApp and one-way reminder SMS messages). Follow-up visits will occur for all participants monthly until Month 3 and then quarterly for 9 months for responders and non-responders randomized to drug level feedback. Non-responders who are randomized to monthly visits will continue to have monthly visits until M9; the month 4, 5, 7, and 8 visits will be special issue counseling visits. We will discontinue all interventions by the month 9 study visit (participants will be exited from two-way SMS and WhatsApp, special issue counseling and drug-level feedback will not occur at the month 9 visit). The primary outcome for the combined intervention is the proportion with high adherence measured by

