6.2. Endpoints

6.2.1.Primary Endpoint

The primary outcome is dried blood spot drug concentrations above 700 fmol/punch at 9 months.

6.2.2.Secondary Endpoints

- TFV-DP concentrations above 700 fmol/punch at 2 months.
- TFV-DP concentrations at 2 and 9 months as a continuous measurement
- Correlates of PrEP adherence at 2 and 9 months, adjusted for study arm.
 - Covariate characteristics assessed at baseline and follow-up will include: Sociodemographic characteristics; partnership characteristics; partner's HIV status; sexual behaviors; HIV risk perception; HIV stigma; PrEP interest; self-efficacy; alcohol and drug use; gender-based violence (GBV); disclosure to peers, family members, teachers, and partner(s) about PrEP use and participation in the study, and level of engagement with the different intervention approaches (e.g., number of SMS messages sent, number of WhatsApp messages sent, satisfaction with intervention received).
- Proportion of young women who discontinue PrEP, timing of discontinuation, and factors associated with PrEP discontinuation.
- Frequency of responding to SMS and WhatsApp messages over follow-up, stratified by “responder” or “non-responder” status after Month 3; content of WhatsApp discussions over follow-up, stratified by “responder” or “non-responder” status after Month
- Qualitative factors that influence women's decisions to use and adhere to PrEP, acceptability of PrEP in the first 2 months after PrEP acceptance, and satisfaction/preferences for the randomized intervention(s) received.
- Qualitative perceptions of our intervention package and opinions on scalability of the interventions from clinic staff and key informants' perspectives.

6.2.3.Exploratory endpoints

- Incident HIV infections, and adherence prior to HIV seroconversion based on drug levels
- Genotypic resistance among incident HIV infections
- Acceptability and feasibility of a urine point-of-care test for drug-level feedback counseling, among the subset of women who accept drug level feedback counseling via a new urine POC assay at their month 9 exit visit.

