- To evaluate (1) the effect of the mHealth interventions on early PrEP adherence (month 2), (2) the effect of the mHealth interventions on long-term PrEP adherence (month 12), and (3) the effect of the additional adherence support interventions on long-term PrEP adherence (month 12) among (a) non-responders to the first-line SMS intervention and (b) non-responders to the first-line WhatsApp intervention.
- To identify correlates of PrEP adherence at the two-, nine- and twelve-month study visits, adjusting for study arm, such as sociodemographic factors, individual-level and partner-level characteristics, and risk practices.
- To assess the proportion of young women who discontinue PrEP, timing of discontinuation, and factors associated with PrEP discontinuation, adjusting for study arm.
- To characterize SMS response rates and the content and frequency of use of WhatsApp groups
- To qualitatively explore factors that influence women's decisions to use PrEP, adhere to PrEP, and their satisfaction with their assigned intervention(s) and preferences for another intervention option.

The exploratory objectives of this study are:

- To assess HIV incidence and the presence of detectable TFV-DP in PrEP users who acquire HIV infection during the study.
- To describe antiretroviral drug resistance among women who acquire HIV infection.

Study Design

This is a single-site sequential multiple assignment randomized trial (SMART) to assess a stepped model of scalable adherence support strategies in young South African women who initiate PrEP.

Women will be consented to have 12 months of follow-up. PrEP will be offered as part of a comprehensive package of sexual and reproductive health care that includes: HIV testing, counseling, condoms, contraception, and testing for and treatment of STIs. Approximately 350 women will be consented and randomized (about 175 participants in each initial intervention arm). Women will receive their assigned interventions until month 9 (the primary endpoint) and will be exited from the SMS and WhatsApp messages at the month-9 visit. They will be followed for an additional three months to assess the intervention's sustained effect on PrEP adherence at month 12.

At enrollment women will be randomly assigned in a 1:1 ratio to receive both standard adherence support counseling with monthly clinic visits and one-way SMS reminder messages and either participation in WhatsApp groups or weekly two-way SMS communication.

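### Protocol 6.4.2 words the time-to-discontinuation comparison as covering only women who stop PrEP, and unequal second-line visit schedules can bias it; the SAP has no analysis that settles either point

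*Protocol*

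**What the plan says.** Protocol 6.2.2 lists the endpoint: "Proportion of young women who discontinue PrEP, timing of discontinuation, and factors associated with PrEP discontinuation". Protocol 6.4.2 gives the only analysis of its timing. "Survival analysis will be used to assess the effect of the adherence strategies as well as individual characteristics", and the sentence ends "on time to PrEP discontinuation for those who choose to stop PrEP before 9 months". Neither document says that women still on PrEP stay in the risk set and are censored. Neither defines discontinuation or how it is dated.

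The SAP (Study Objectives and Hypotheses) keeps the objective: "To assess the proportion of young women who discontinue PrEP, timing of discontinuation, and factors associated with PrEP discontinuation, adjusting for study arm". Its Data Analysis section has Primary Analyses 1 to 3, Secondary Analyses 1 to 4 and Exploratory Analyses 1 and 2. None is a discontinuation analysis. The nearest item is a summary, within Primary Analysis 1, of reasons for stopping among women who did not return in months 1 to 3.

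On visits, Protocol 4.2.4.1 states: "Women who are randomized to continue monthly visits will have visits at months 4, 5, 7, and 8 that are focused on counseling". Section 6.1 agrees: "Non-responders who are randomized to monthly visits will continue to have monthly visits until M9". Appendix IA marks an adherence assessment and drug supply at those extra visits, and Section 4.2.5 has PrEP dispensed at them. Under Section 4.2.4.2 the drug-level-feedback arm moves to quarterly visits.

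The word is also used for a temporary interruption. Section 4.6 says "PrEP will be discontinued during the one month of PEP, and restarted following repeat HIV testing".

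**The concern.** The stated purpose is to assess the effect of the strategies. A comparison confined to stoppers asks which of them stopped sooner. The question of interest is which strategy keeps women on PrEP, and that depends mainly on how many stop. Every woman in a stoppers-only analysis has the event, so a strategy that prevents stopping gets almost no credit.

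The second problem concerns detection. From month 3, scheduled visits fall at months 4, 5, 6, 7, 8 and 9 in the monthly arm and at months 6 and 9 in the feedback arm. If the date of stopping is the visit at which it is found, the monthly arm appears to stop earlier even when behaviour is the same. The error would count against monthly visits.

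**Working it through.** The documents give no event count, hazard ratio or power for this analysis, so there is no stated figure to reproduce.

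**Inputs from the documents.** 175 women per first-line arm (Protocol 6.3). 166 to 184 re-randomized women (Table 2), allocated 1:1, so 83 to 92 per arm. Second-line window: months 3 to 9, six months.

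**Assumptions.** Constant hazards, the stopping rates shown, two-sided 0.05 log-rank tests and, in step 2, a stop dated to the next scheduled visit.

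**Step 1: stoppers only, first-line size, exact dates.**

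- Hazard over T = 9 months: λ = −ln(1 − p)/T. For 30% vs 50% stopping, true HR = ln 0.70 / ln 0.50 = 0.357/0.693 = 0.51.
- All women: expected events = 175 × 0.30 + 175 × 0.50 = 140. Then |ln HR| × √140 / 2 = 0.664 × 5.92 = 3.93, and 3.93 − 1.96 = 1.97, so power is about 97.6%.
- Stoppers only: mean stopping time is 1/λ − T(1 − p)/p. For p = 0.30 this is 25.23 − 21.00 = 4.23 months; for p = 0.50 it is 12.98 − 9.00 = 3.98 months. A 20-point difference in stopping has become a quarter of a month.

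Simulation agrees (ranges are across independent runs):

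| Stop by month 9 | All women: HR, power | Stoppers only: HR, power |
|---|---|---|
| 30% vs 50% | 0.51–0.52, 97–99% | 0.91–0.92, 7–12% |
| 40% vs 60% | 0.56, 97% | 0.89–0.90, 9–12% |

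**Step 2: unequal visits, second-line comparison, all women at risk, no true difference.**

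Take 50% stopping between months 3 and 9. The true mean stop is 8.66 − 6.00 = 2.66 months after month 3. The mean wait to the next visit is 0.51 month on the monthly schedule, which gives a recorded mean at month 3 + 2.66 + 0.51 = 6.2. On the quarterly schedule, (1 − √0.5)/0.5 = 58.6% of stops are recorded at month 6 and 41.4% at month 9, so the mean is 6 × 0.586 + 9 × 0.414 = month 7.2.

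| Stop, months 3 to 9 (both arms) | HR, monthly vs feedback | False-positive rate |
|---|---|---|
| 30% | 1.08–1.10 | 5–6% |
| 50% | 1.18 | 11–14% |
| 70% | 1.33 | 42–47% |

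A real benefit is diluted: with N = 166, a true HR of 0.51 appears as 0.61, and power falls from 75% to 57%.

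**Step 3: the remedy, N = 166.** With all women at risk and stops scored at months 6 and 9 in both arms, the null HR is 1.00 and the false-positive rate 4.5 to 4.8% (30 to 60% stopping). For true HRs of 0.51 and 0.56, power is 74% and 76%, against 75% and 76% with exact dates.

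**The case against.** The strongest reply is that the clause in 6.4.2 is loose drafting. It may define the event as voluntary stopping before month 9, as distinct from seroconversion, toxicity holds or a PEP interruption. Survival analysis normally censors women without the event, and the listed proportion who discontinue needs continuers in its denominator. That reading is possible, and step 1 does not apply under it. But no passage states it, and the SAP does not supply it.

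On detection, visits are not the only source of information. Women assigned to two-way SMS keep weekly contact with call-back in both second-line arms (4.2.1.3). Interim contacts are documented (4.2.6), missed visits are followed up (4.8) and withdrawal reasons are recorded (4.9). Dating by reported last dose would shrink the bias, and at 30% stopping it is near nil in any case. All of this stands, so the size of the bias is conditional. Section 6.4.2 also plans weighting if loss to follow-up depends on covariates, but that does not address visit frequency.

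Section 4.4 gives a single three-bottle dispensing schedule at months 3 and 6 with no exception for the monthly arm, whereas 4.2.5 has monthly dispensing there. These passages need reconciling before refill records are used for dating. The visit schedules differ either way.

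A reader might infer that the trial cannot show which strategy keeps women on PrEP. The documents do not support that. SMS and WhatsApp women follow the same visit rule, and the proportion stopping and TFV-DP at the common month 9 visit both inform persistence.

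**Conclusion.** The point holds as a specification fault in one secondary analysis. Read literally, the sentence selects on the outcome and removes most of any strategy effect: under the assumed stopping rates, power drops from about 97–99% to 7–12%. Read as an event definition, it is incomplete, and nothing in the SAP completes it.

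The visit-schedule bias is separate. It affects the second-line comparison and the embedded strategies built on it, and it depends on next-visit dating, which neither document states. It is negligible at 30% stopping, moderate at 50% and serious at 70%. The documents do not say which rate to expect.

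A reader might also combine the two problems and conclude that the analysis will point the wrong way. With stoppers only and next-visit dating (N = 166), a true HR of 0.51 or 0.56 does appear as about 1.73, significant in the wrong direction in 86 to 92% of runs. But this needs both the literal reading and the unstated dating rule, so it is a worst case and not a prediction. The primary endpoint is untouched.

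**What to change.** Replace the sentence in Protocol 6.4.2 and add a discontinuation analysis to the SAP.

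- **First-line comparison.** All randomized women at risk from enrolment; women still on PrEP censored at month 9. Use the visits common to all women, including months 1 and 2, because the protocol expects heavy early drop-out.
- **Second-line comparison.** All re-randomized women still on PrEP at month 3, at risk from month 3. Score stopping in both arms at months 6 and 9, or use an interval-censored model.
- **Women already off PrEP at month 3.** Missed refills at month 1 or 2 qualify a woman for re-randomization, so some will have stopped by then. State a rule for them that is identical in both arms; for example, also report the proportion off PrEP at month 9 among all re-randomized women.
- **Definitions.** State how discontinuation is dated, and how the analysis counts loss to follow-up (with a sensitivity analysis), temporary holds followed by restart, and seroconversion.

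The cost is wording and a little more analysis work on visit and pharmacy records already collected. The downside is coarser timing in the monthly arm. In the simulation with N = 166, the common schedule lost at most about 2 points of power.

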7.0 HUMAN SUBJECTS CONSIDERATIONS

8.1. Ethical Review

The protocol, ICF, participant education and recruitment materials, and other requested documents — and any subsequent modifications — will be reviewed and approved by the ethical review bodies responsible for oversight of research conducted at the study site. Subsequent to initial review and approval, the responsible IRBs/ECs will review the protocol at least annually.

8.2. Informed Consent

Written informed consent will be obtained from each study participant. The ICFs describe the purpose of the study, the procedures to be followed, and the risks and benefits of participation, in accordance with all applicable regulations. The ICF will be translated into local languages and the accuracy of the translation will be verified by performing an independent back-translation. The site will assess literacy

in one of the study languages as described in study specific SOPs. Participants will be provided with a copy of their ICFs if they are willing to receive them.

8.3. Study oversight

This study will be subject to oversight by an independent data monitoring committee that will periodically review data from the study, including study execution, adherence, HIV incidence, HIV drug resistance and serious adverse events. The independent data monitoring committee will provide recommendations to the study team as part of approximately six-monthly reviews. Reports from all reviews will be provided for submission to overseeing IRB/ECs.

8.4. Risks

Phlebotomy

Venipuncture is sometimes associated with discomfort. Phlebotomy may lead to discomfort, dizziness, bruising, swelling, and rarely, an infection at the venipuncture site.

HIV and STI Testing

Staff will instruct women in obtaining self-collected vaginal swabs for STI testing. Participants may become embarrassed, worried, or anxious when completing their HIV risk assessment and/or receiving HIV counseling. They also may become worried or anxious while waiting for their HIV and STI test results. Individuals who learn that they have an STI or HIV infection may experience anxiety or depression related to their test results. Trained counselors will be available to help participants deal with these feelings.

Sensitive Questions

Participants will be asked questions about their sexual behavior that may make them feel uneasy. Participants do not have to answer any question that they do not want to and can stop answering the questions at any time.

Confidentiality

Although the study site will make every effort to protect participant privacy and confidentiality, it is possible that participants' involvement in the study could become known to others, and that social harms may result (e.g., because participants could become known as at "high risk" for HIV infection). For example, participants could be treated unfairly or discriminated against, or could have problems being accepted by their families and communities.

Mobile Phones, SMS, and WhatsApp

For participants who are randomized to participate in two-way SMS texting and WhatsApp groups to support PrEP adherence, it is possible that timing or volume of messages will be inconvenient to participants or may exceed cell phone plan limits and obligate participants' to pay for them. The site will develop a system to provide compensation for mobile phone charges and data limits to participants.

Information entered by participants into mobile phone programs will be maintained on a secure server via a secure, password-protected log-in. However, it is possible that someone who has access to the participant's phone may see this information, revealing participation in the study. Lost or stolen phones are a practical reality. To mitigate these risks, participants will be trained to secure their phones with a password or PIN and to delete old messages. Messages will not disclose individual level information so that if accessed will not compromise confidentiality around health status or medication use.

Participants may be at risk of confidentiality breaches if a third party gains access to a participant's phone and views the WhatsApp communications. Participants may also receive unwanted comments from other group members. We will establish group norms prior to WhatsApp group enrollment and will inform all participants of these norms. A group facilitator will monitor the WhatsApp groups regularly for violations

of group norms or rules and will exit participants from the WhatsApp group who commit such violations. Participant identities may also become known if they have a photo linked to their WhatsApp account. We will ensure that all participants are aware of these risks of participating in the WhatsApp group during the informed consent process. Finally, participants will be able to send personal messages directly to the group administrator to discuss any concerns or issues privately and they will be informed during the consent process that they can reply “STOP” to any SMS messages or remove themselves from the WhatsApp group if they wish to discontinue messages.

Study Drug Side Effects

All participants who experience side effects or other clinical events during the study will receive follow-up by study staff. If treatment is required beyond the capacity of the study staff, study clinicians will refer the participant to appropriate services or organizations that can provide appropriate care.

HIV drug resistance in HIV seroconverters

It is possible that a participant who is taking PrEP and becomes infected with HIV during this study may develop resistance to FTC/TDF. Multiple steps will be taken to minimize the risk of drug resistance. HIV testing will be performed at Enrollment, Month 1 and quarterly for all participants. Persons with acute viral syndromes that may reflect acute HIV infection will have study enrollment delayed for two weeks at which time they will have additional HIV testing. If acute HIV infection is suspected after Enrollment for any participant accepting PrEP, the participant will undergo evaluation. These steps should minimize the risk of drug resistance occurrence by identifying HIV infection in its early stages and stopping study drug. If any participant becomes HIV-infected during the study and develops TDF or FTC resistance, an alternative treatment regimen could be used that is not impacted by resistance to these drugs. If a participant becomes infected during the study, real-time resistance testing will be conducted for clinical management.

